8.2 Serious Adverse Events

Any SAE that is ongoing at the end of the study (Day 60) will be followed by the Investigator until the SAE has subsided or until the condition(s) becomes chronic in nature, until the patient begins alternative treatment for COVID-19, until the condition(s) stabilizes (in the case of persistent impairment), or until the patient dies.

An AE or adverse reaction is considered serious if, in the view of either the Investigator or Sponsor, it results in any of the following outcomes:

- Death;
- A life-threatening AE;

Note: An AE or adverse reaction is considered “life-threatening” if, in view of either the Investigator or Sponsor, its occurrence places the patient at immediate risk of death. It does not include an event that, had it occurred in a more severe form, might have caused death.

- Requires hospitalization or prolongation of existing hospitalizations;

Note: Any hospital admission with at least 1 overnight stay will be considered an inpatient hospitalization. An emergency room or urgent care visit without hospital admission will not be recorded as an SAE under this criterion, nor will hospitalization for a procedure scheduled or planned before signing of informed consent, or elective treatment of a pre-existing condition that did not worsen from baseline (ie, Day 1 [Visit 2]). However, unexpected complications and/or prolongation of hospitalization that occur during elective surgery should be recorded as AEs and assessed for seriousness. Admission to the hospital for social or situational reasons (ie, no place to stay, live too far away to come for hospital visits, respite care) will not be considered inpatient hospitalizations.

- A persistent or significant disability/incapacity or substantial disruption of the ability to conduct normal life functions;
- A congenital anomaly/birth defect; or
- An important medical event.

Note: Important medical events that do not meet any of the above criteria may be considered an SAE when, based upon appropriate medical judgment, they may jeopardize the patient and may require medical or surgical intervention to prevent one of the outcomes listed above. Examples of such medical events include allergic bronchospasm requiring intensive treatment in an emergency room or at home, blood dyscrasias or convulsions that do not result in inpatient hospitalizations, or the development of drug dependency.

As events of progression of the patient’s underlying COVID-19 diagnosis will be captured as efficacy endpoints (see Section 7.1), these events should not be reported as SAEs unless considered related to the study drug or a study procedure or if the outcome is fatal during the study and within the safety reporting period. Examples of events that are expected in the course of ARDS are provided above in Section 8.1.4. If the event has a fatal outcome during the timeframe, the event of “Progression of COVID-19” must be recorded as an SAE with a fatal outcome.

8.3 Serious Adverse Event Reporting – Procedures for Investigators

Initial reports

All SAEs occurring from the time of the first dose of study drug until Day 60 (approximately 30 days following the last dose of study drug) must be reported to Medpace Clinical Safety within 24 hours of the knowledge of the occurrence. After the 30-day reporting window, any SAE that the Investigator considers related to study procedures must be reported to the Medpace Clinical Safety or the Sponsor/designee.

To report the SAE, complete the SAE form electronically in the electronic data capture (EDC) system for the study. When the form is completed, Medpace Safety personnel will be notified electronically by the EDC system and will retrieve the form. If the event meets serious criteria and it is not possible to access the EDC system, send an email to Medpace Safety at [contact] or call the Medpace SAE reporting line (telephone number listed below), and fax/email the completed paper SAE form to Medpace (contact information listed in Section 8.6) within 24 hours of awareness. When the EDC system becomes available, the SAE information must be entered within 24 hours of the system becoming available.

Follow-up reports

The Investigator must continue to follow the patient until the SAE has subsided or until the condition(s) becomes chronic in nature, stabilizes (in the case of persistent impairment), or the patient dies.

Within 24 hours of receipt of follow-up information, the Investigator must update the SAE form electronically in the EDC system for the study and submit any supporting documentation (eg, patient discharge summary or autopsy reports) to Medpace Clinical Safety via fax or email. If it is not possible to access the EDC system, refer to the procedures outlined above for initial reporting of SAEs.

8.4 Pregnancy Reporting

If a patient becomes pregnant during the study or within the safety follow-up period defined in the protocol, the Investigator is to stop dosing with study drug(s) immediately and the patient should be withdrawn from the study. Early Termination Visit procedures should be implemented at that time.

A pregnancy is not considered to be an AE or SAE; however, it must be reported to Medpace Clinical Safety within 24 hours of knowledge of the event. Medpace Clinical Safety will then provide the Investigator/center the Exposure In Utero (EIU) form for completion. The Investigator/center must complete the EIU form and fax/email it back to Medpace Clinical Safety.

If the female partner of a male patient becomes pregnant while the patient is receiving study drug or within the safety follow-up period defined in the protocol, the Investigator should notify Medpace Clinical Safety as described above.

The pregnancy should be followed until the outcome of the pregnancy is known, whenever possible. Once the outcome of the pregnancy is known, the EIU form should be completed and faxed/mailed to Medpace Clinical Safety. If the outcome of the pregnancy meets the criteria for immediate classification as an SAE (ie, postpartum complication, spontaneous abortion, stillbirth, neonatal death, or congenital anomaly), the Investigator should follow the procedures for reporting an SAE.

8.5 Expedited Reporting

The Sponsor/designee will report all relevant information about Suspected Unexpected Serious Adverse Reactions (SUSAR) that are fatal or life-threatening as soon as possible to the Food and Drug Administration (FDA), and in any case no later than 7 days after knowledge by the Sponsor/designee of such a case. Relevant follow-up information will subsequently be communicated within an additional 8 days.

All other SUSARs will be reported to the FDA as soon as possible but within a maximum of 15 days of first knowledge by the Sponsor/designee.

The Sponsor/designee will also report any additional expedited safety reports required in accordance with the timelines outlined in country-specific legislation.

The Sponsor/designee will also inform all Investigators as required per local regulation.

The requirements above refer to the requirements relating to investigational medicinal product.

8.6 Special Situation Reports

Special situation reports include reports of overdose, misuse, abuse, medication error, and reports of adverse reactions associated with product complaints.

- **Overdose:** Refers to the administration of a quantity of a medicinal product given per administration or cumulatively (accidentally or intentionally), which is above the maximum recommended dose according to the protocol. Clinical judgment should always be applied. In cases of a discrepancy in the drug accountability, overdose will be established only when it is clear that the patient has taken additional dose(s) or the Investigator has reason to suspect that the patient has taken additional dose(s);
- **Misuse:** Refers to situations where the medicinal product is intentionally and inappropriately used not in a way that is not in accordance with the protocol instructions or local prescribing information and may be accompanied by harmful physical and/or psychological effects;
- **Abuse:** Is defined as persistent or sporadic, intentional excessive use of a medicinal product, which is accompanied by harmful physical or psychological effects;
- **Medication error:** Is any unintentional error in the prescribing, dispensing, or administration of a medicinal product by a healthcare professional, patient, or consumer, respectively. The administration or consumption of the unassigned treatment and administration of an expired product are always reportable as medication errors, cases of patients missing doses of study drug are not considered reportable as medication error; and
- **Product complaint:** Is defined as any written, electronic, or oral communication that alleges deficiencies related to the identity, quality, durability, reliability, safety, effectiveness, or performance of a drug or device after it is released for distribution. A special situations form will only be completed if a complaint is associated with an adverse drug reaction.

All special situation events as described above must be reported on the Special Situations Report form and faxed/mailed to Medpace Clinical Safety (contact information listed below) within 24 hours of knowledge of the event. All AEs associated with these Special Situation reports should be reported as AEs or SAEs as well as recorded on the AE eCRF and/or the SAE report form. Details of the symptoms and signs, clinical management, and outcome should be provided, when available.

Safety Contact Information: Medpace Clinical Safety

8.7 Safety Endpoints

The safety endpoints include the following:

- AEs and SAEs;
- Clinical laboratory assessments (including clinical chemistry, hematology, and urinalysis);
- Vital signs;
- Physical examinations; and
- 12-lead ECGs.

8.8 Clinical Laboratory Assessments

Samples for blood chemistry and hematology will be obtained as indicated in Appendix A. See Appendix B for a complete list of analytes. If any additional laboratory evaluations are performed for standard of care, these data should be entered into the eCRF. If a blood chemistry or hematology assessment was performed within 24 hours prior to the first dose of study drug, it is not necessary to repeat the assessment on Day 1. Effort should be made to obtain blood chemistry and hematology at approximately the same time on each day as indicated in Appendix A; however, it should not be considered a protocol deviation if this is not possible.

Samples for urinalysis will be obtained as indicated in Appendix A. See Appendix B for a complete list of analytes.

Screening and eligibility laboratory assessments may be performed at the local laboratory. All other laboratory assessments during the study will be assessed by a central laboratory.

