Standard of care procedures for mechanical ventilation (eg, low tidal volume protective mechanical ventilation) and standard of care procedures for weaning from mechanical ventilation will be followed. The clinical criteria for weaning readiness testing and discontinuation from mechanical ventilation are described in Appendix D.

Study drug administration will begin on Day 1 (Visit 2) following randomization. All patients will receive standard of care and/or EUA treatment for COVID-19 in addition to the study drug. Patients will continue study drug treatment BID through Day 27 and take 1 dose on Day 28. If a patient is discharged from the hospital prior to Day 28, he/she will continue treatment as an outpatient at home with his/her assigned treatment (FP-025 100 mg BID, FP-025 300 mg BID, or placebo BID) until Day 28. Dosing instructions will be provided prior to discharge. Although treatment will be identical for inpatients and outpatients, patients discharged from the hospital will follow a different Schedule of Procedures, characterized by telemedicine (or telephone, if sites and/or patients do not have video capability) visits. The End of Treatment (EOT) Visit on Day 28

will be identical for all patients (with the exception of the arterial oxygen partial pressure [PaO₂]/fractional inspired oxygen [FiO₂] ratio, performed only in patients on invasive or non-invasive ventilation) and will include a high-resolution, non-contrast CT scan, in addition to other assessments.

After treatment is completed, all patients will undergo 2 follow-up assessments during the Follow-Up Period. The first follow-up will be a telephone visit on Day 45 to assess concomitant medications, adverse events (AEs), and the NIAID 8-point ordinal scale for COVID-19 and hospitalization outcomes score. The second follow-up will be an in-person visit on Day 60 and will include a high-resolution, non-contrast CT scan and pulmonary function tests, in addition to other assessments.

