4.2 Exclusion Criteria

Patients who meet any of the following criteria will be excluded from participation in the study:

1. Is not expected to survive more than 24 hours;
2. Is on extracorporeal membrane oxygenation (ECMO) at the Screening Visit;
3. Has an underlying clinical condition where, in the opinion of the Investigator, it would be extremely unlikely that the patient would come off ventilation (eg, motor neuron disease, Duchenne muscular dystrophy, or rapidly progressive pulmonary fibrosis);
4. Has a known history of idiopathic pulmonary fibrosis or interstitial lung disease as defined by the American Thoracic Society 2018 guidelines;²³
5. Has known active tuberculosis (TB), a history of incompletely treated TB, and/or suspected or known extrapulmonary TB;
6. Has Child-Pugh Class B or C active liver disease or an alanine aminotransferase or aspartate aminotransferase level $>4 \times$ the upper limit of normal at the Screening Visit;
7. Has moderate to severe renal insufficiency, defined as an estimated glomerular filtration rate (eGFR) ≤ 30 mL/min/1.73 m², at the Screening Visit or requires hemodialysis;
8. Has a malignant tumor (excluding a malignant tumor cured with no recurrence in the past 5 years, completely resected basal cell and squamous cell carcinoma of skin, and/or completely resected carcinoma in situ of any type);
9. Has an uncontrolled systemic or local autoimmune or inflammatory disease besides COVID-19;
10. Has evidence of an active concurrent non-COVID-19 pneumonia that requires additional antimicrobial treatment at the time of the Screening Visit and is caused by a known or suspected bacterial pathogen, respiratory syncytial virus (RSV), influenza virus, SARS-CoV-1, MERS-CoV, aspergillus, mucormycosis-causing fungi, or other pulmonary pathogen(s);
Note: If a viral respiratory panel has not been collected within the 24 hours prior to the Screening Visit, a viral respiratory panel will be administered at the Screening Visit to determine eligibility. At a minimum, the panel will evaluate for RSV, influenza A, and influenza B.
11. Has received any other investigational therapeutic products within 4 weeks or 5 half-lives, whichever is longer, prior to randomization;

12. Has a known history of HIV, hepatitis B, or hepatitis C infection;
13. Has a known serious allergic reaction or hypersensitivity to any components of FP-025;
14. Is pregnant or breastfeeding;
15. Has a history of drug or alcohol abuse within the past 2 years;

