7.1.3 Other Secondary Efficacy Endpoints

The other secondary efficacy endpoints include the following, with each dose (Phase 2) or the optimal dose (Phase 3) of FP-025 compared to placebo:

- Quantitative assessment of lung fibrosis at Day 28 and at Day 60 using high-resolution, non-contrast CT scan;
- Proportion of patients who were randomized on invasive mechanical ventilation who are free of invasive mechanical ventilation at Day 28 and at Day 60;
- Number of ventilator-free days (ie, days free of invasive mechanical ventilation) at Day 28 and at Day 60;
- Number of ICU-free days at Day 28 and at Day 60;
- Number of days in the hospital at Day 28 and at Day 60;
- Change from baseline in peripheral capillary oxygen saturation (SpO₂) at Day 28 and at Day 60;
- Change from baseline in PaO₂/FiO₂ ratio at Day 28 and at Day 60 (patients on invasive or non-invasive ventilation only);
- Proportion of patients alive and not hospitalized at Day 28 and at Day 60;

- Proportion of patients with disease progression (defined as a ≥ 2 -point decrease in the NIAID 8-point ordinal scale score or death) at Day 28 and at Day 60;
- Proportion of patients who improve by ≥ 2 points on the NIAID 8-point ordinal scale scores at Day 28 and proportion of patients who improve by ≥ 2 points at Day 60;
- Pulmonary function at Day 28 (if possible based on the patient's clinical condition per the judgment of the Investigator) and at Day 60 (all patients) based on the following scores:
 - Forced vital capacity (FVC);
 - Forced expiratory volume in 1 second (FEV₁);
 - FEV₁/FVC ratios; and
 - Diffusing capacity of the lungs for carbon monoxide; and
- Change from baseline in eGFR, blood urea nitrogen, and serum creatinine at Day 28 and Day 60.

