APPENDIX B: CLINICAL LABORATORY ANALYTES

Screening and eligibility laboratory assessments may be performed at the local laboratory. All other laboratory assessments during the study will be assessed by a central laboratory.

Standard Safety Chemistry Panel

Alanine aminotransferase	Albumin
Alkaline phosphatase	Amylase
Aspartate aminotransferase	Bicarbonate
Blood urea nitrogen	Calcium
Chloride	Creatine kinase
Creatinine	Estimated glomerular filtration rate
Gamma-glutamyl transferase	Glucose
Inorganic phosphorus	Lactate dehydrogenase
Lipase	Potassium
Sodium	Total bilirubin
Total protein	Uric acid

Endocrinology

Human chorionic gonadotropin (hCG) [1]

1. hCG will be performed in women of childbearing potential only.

Hematology

White blood cell count and differential [1]

1. Manual microscopic review will only be performed only if white blood cell count and/or differential values are out of reference range.

Severe Acute Respiratory Syndrome Coronavirus-2 Testing

Reverse transcriptase polymerase chain reaction (PCR) for severe acute respiratory syndrome (SARS) coronavirus (CoV)-2 or equivalent test [1]

1. SARS-CoV-2 reverse transcriptase PCR may be performed at the Screening Visit, if not done previously. The patient must have a documented, laboratory-confirmed SARS-CoV-2 infection as determined by reverse transcriptase PCR (or an equivalent test) immediately prior to or during the current hospitalization.

Viral Respiratory Panel [1]

Respiratory syncytial virus

1. Additional viruses may be tested for at the Investigator's discretion and based on local laboratory panels. Actual viruses tested for may vary depending on local standards of care.
2. Influenza A may include H1 and H3 subtypes.

Urinalysis

Bilirubin	Blood
Creatinine	Glucose
Ketones	Leukocyte esterase
Microscopy [1]	Nitrite
pH	Protein
Specific gravity	Urine albumin to creatinine ratio
Urobilinogen	

1. Microscopy will only be performed as needed based on positive dipstick test results.

Inflammatory and Fibrotic Biomarkers [1]

C-reactive protein	C4M
C6M	Connective tissue growth factor
CRPM	Cytokines [2]
Ferritin	MMP-7
MMP-9	MMP-12
PRO-C3	PRO-C4
PRO-C6	reC1M
Transforming growth factor-β	X-FIB (D-dimer)

1. Additional biomarkers not listed here may be evaluated at a future date.
2. Cytokines evaluated will include interferon-γ, tumor necrosis factor-α, IL-6, IL-1β, and C-C motif chemokine ligand 2 (monocyte chemoattractant protein-1).

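### The 24-hour waiver in Section 8.8 can leave a local-laboratory value as the only baseline for renal change scores whose later values are central

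*Combined protocol and SAP*

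**What the plan says.** Section 8.8 contains two rules that meet at baseline.

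- The waiver: a chemistry or hematology assessment "performed within 24 hours prior to the first dose of study drug, it is not necessary to repeat the assessment on Day 1". No condition is placed on the laboratory that ran it.
- The laboratory rule: "Screening and eligibility laboratory assessments may be performed at the local laboratory", and then "All other laboratory assessments during the study will be assessed by a central laboratory". Appendix B repeats this rule.

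Section 7.1.3 lists among the other secondary efficacy endpoints "Change from baseline in eGFR, blood urea nitrogen, and serum creatinine at Day 28 and Day 60". This endpoint serves the renal-function objective in Section 2.2.

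Section 7.1.4 fixes the biomarker baseline as the pre-dose Day 1 value. Section 7.1.3 gives no such definition for the renal measures, and no eGFR equation is named. Section 9.2.1.2 leaves the analysis of other secondary endpoints to the SAP, and the text reviewed here contains no SAP rule on the matter.

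**The concern.** A change score is only as good as the comparability of its two measurements. If the baseline comes from a hospital laboratory and the later value from the central one, any difference in assay calibration or eGFR equation enters that patient's change score. Across sites this adds variance to the comparison of FP-025 with placebo. If local laboratories read higher or lower than the central one on average, it also moves the mean change within each arm, so part of an apparent rise or fall in renal function could be a laboratory artefact.

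The omission has to be dealt with before enrollment. An analysis plan can choose among recorded values, but it cannot supply a central pre-dose sample that was never drawn.

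**Working it through.** The plan gives no figure on this point, so there is none to reproduce. The check has two parts: whether the text allows the mismatch, and how large its effect could be.

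**Tracing the text**

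1. Table 2 places the Screening Visit on Study Day -1 to 1. Under Section 3.1.1, "Study drug administration will begin on Day 1 (Visit 2) following randomization". A screening sample can therefore fall within 24 hours before the first dose.
2. Exclusion criterion 7 (Section 4.2) needs an eGFR result at screening. Appendix B lists eGFR, BUN and creatinine in the chemistry panel, which the waiver covers.
3. That screening sample may be local. If the site also uses the waiver, no central pre-dose chemistry exists.
4. Day 28 and Day 60 chemistry falls under the rule for all other assessments and is central.
5. Both steps are optional. A site that runs screening centrally, or that draws the Day 1 sample scheduled in Table 2, has central values throughout.

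So the mismatch is permitted, and it arises where a local screening result is used and the Day 1 draw is skipped. The share of patients, *f*, is not in the documents.

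**Illustrative size**

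The inputs are assumptions, because the documents give no assay or variability figures:

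- σ, the SD of true eGFR change: 20 to 25 mL/min/1.73 m²
- s, the SD of the local-minus-central offset between laboratories: 5 to 10 mL/min/1.73 m²
- an offset independent of the true change, and a raw change score as the analysed quantity

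*Every patient affected (f = 1).* Relative increase in variance = s²/σ². The interval widens by √(1 + s²/σ²) − 1.

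| s | σ | s²/σ² | Interval wider by |
|---|---|---|---|
| 5 | 25 | 25/625 = 4% | √1.04 − 1 ≈ 2% |
| 5 | 20 | 25/400 ≈ 6% | √1.0625 − 1 ≈ 3% |
| 8 | 20 | 64/400 = 16% | √1.16 − 1 ≈ 8% |
| 10 | 20 | 100/400 = 25% | √1.25 − 1 ≈ 12% |

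*A share f affected.* With no mean offset, the increase is f·s²/σ². At f = 0.5 it is 2% to 12.5%. A mean offset b adds f(1 − f)·b²/σ², because affected and unaffected patients then differ on average. With b = s = 10, σ = 20 and f = 0.5, the total is 0.5 × 0.25 + 0.25 × 0.25 = 0.1875, or about 19%.

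*Within-arm mean change.* The shift has size f·b in each arm. In units of σ, for f from 0.25 to 1 and b from 0.1 to 0.5, it runs from 0.025 to 0.50.

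*Between arms.* The rule is the same in both blinded arms, so the expected difference is 0. Chance imbalance in waiver use has SD b·√(2f(1 − f)/n). At f = 0.5 and b = 0.5σ this is about 0.06σ with 33 per arm (Phase 2, 99/3) and 0.03σ with 152 per arm (Phase 3).

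**The case against.** The strongest reply is that this is a sensible economy with little at stake. Accepting a recent result spares a repeat draw in very ill patients. Local testing and the waiver are both optional, and Table 2 still schedules Day 1 laboratory work. The endpoint is a comparison with placebo, so a common offset cancels in expectation. It is outside the Phase 3 hierarchy in Section 9.2.1.3, Phase 2 is not powered, and the primary and key secondary endpoints are untouched. The SAP could recompute eGFR by one equation from recorded creatinine, or restrict the analysis to patients with central values at both times.

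Most of that stands, and it limits the weight of the point. It does not remove it. Recomputing eGFR settles the equation but not a calibration difference in creatinine, and it does nothing for BUN. Restricting to central pairs drops randomized patients.

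Three stronger readings are tempting and are not supported:

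- *Most patients are affected.* The screening window shows that many could qualify. It does not show how many sites would test locally and then skip the draw.
- *The treatment comparison is biased.* Nothing in the rule differs by arm.
- *Laboratory shift tables in the safety report are distorted.* Section 9.2.2 says only that laboratory data will be summarized and specifies no shift or change-from-baseline table.

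**Conclusion.** The point holds in a limited form. Section 8.8 permits a local baseline to be set against central Day 28 and Day 60 values for eGFR, BUN and creatinine, and no section reviewed prevents it or fixes the renal baseline. The effect is added noise in the comparison and a possible offset in within-arm mean change, with no expected bias between arms and no effect on the primary endpoint.

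The range of 4% to 25% more variance (interval about 2% to 12% wider) is an illustration. It rests on assumed SDs and on every patient being affected, so a reader should not take it as an estimate for this trial. It falls in proportion to uptake when there is no mean offset. A baseline-adjusted model, which the documents neither specify nor rule out, would give other figures.

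The change is worth making because it is cheap, it serves a stated secondary objective, and a missing central baseline cannot be recovered later.

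**What to change.** - In Section 8.8, limit the 24-hour waiver to results from the central laboratory. Otherwise, send the Day 1 chemistry and hematology sample scheduled in Table 2 to the central laboratory, and state that it is drawn before the first dose. Table 2 and its footnote give no pre-dose timing for these tests, so this must be added. Local results continue to decide eligibility, so randomization does not wait.
- Pair the draw with the pre-dose Day 1 biomarker sample (Section 7.1.4). Day 1 PK sampling is a less dependable anchor, because Section 7.1.5 moves it to Day 2 for patients randomized in the afternoon.
- In Section 7.1.3, define the renal baseline as the last central pre-dose value, with eGFR calculated by one equation at all time points.
- For any patient enrolled under the present rule, record the laboratory source of the baseline and add a sensitivity analysis limited to central pairs.

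The cost is a few mL of blood and one shipment for each patient who would otherwise have used the waiver.
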